8.0 STATISTICAL ANALYSIS PLAN

8.1 Statistical Analysis Plan Summary

This is a Phase II open-label study designed to evaluate the safety and efficacy of the combination of MK3475 and 5-azacitidine in patients with MDS. Two different patient groups (hypomethylating failure group and previously untreated MDS group) will be studied. Each cohort will be composed of N=20 patients. Accrual will be parallel for each patient group.

The primary efficacy outcome for each cohort is the overall response rate (ORR) defined as CR + PR + hematological improvement (HI). Overall response will be assessed after 6 cycles of treatment; cycle length is 28 days. A maximum of 20 patients will be enrolled in each cohort (total for study N=40).

Hypomethylating failure MDS cohort

The target ORR with the experimental treatment is 20%. There is no standard treatment for this patient population, we use a null ORR of 5%. The regimen of the experimental treatment will be considered worthy of further investigation if it elicits an increase in ORR to 20% with acceptable toxicity. A >30% therapy related non-hematological grade 3/4 toxicity rate is considered unacceptable. Thus, interim monitoring rules, assuming the prior distributions below, were constructed that meet the following two conditions,

- 1) Stop if $\text{Prob}\{p(\text{ORR}, E) < p(\text{ORR}, H) + 0.15 \mid \text{data}\} > 0.99$, or
- 2) Stop if $\text{Prob}\{p(\text{TOX}, E) > 0.30 \mid \text{data}\} > 0.95$,

where $p(\text{ORR}, E)$ and $p(\text{TOX}, E)$ are the true ORR and toxicity rates for the combination treatment, and $p(\text{ORR}, H)$ is the true ORR rate of the standard treatment. The first rule provides for stopping the study if the data suggest that it is unlikely (i.e., probability < 1%) that ORR rate of the experimental treatment is greater than the ORR rate of standard treatment by 15%. The second condition will stop the study early if excessive therapy-related non-hematological grade 3/4 toxicity (>30%) is highly probable (i.e., probability >95%) for the experimental treatment. Monitoring for toxicity and futility will start with the first patient, and cohort size of 5.

The monitoring rule for the toxicity rate, based on these assumptions and monitoring conditions above is found in Table 8. For example, accrual will cease if 4 or more patients experience toxicities among the first 5 patients.

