Table 8. Stop accrual if the number of drug-related non-hematological grade 3/4 toxicities is greater than or equal to indicated (i.e., # patients with toxicities) among the number of patients evaluated				
# patients evaluated	5	10	15	20
# patients with toxicities	4-5	6-10	8-15	Always stop

Monitoring the ORR rate, based on the above assumptions and monitoring conditions is found in Table 9. For example, accrual will cease if no patients experience an overall response within 6 cycles in the first 10 patients treated.

Table 9. Stop accrual if the number with response is less than or equal to indicated (i.e., # patients with overall response) among the number of patients evaluated			
# patients evaluated	5	10-15	20
# patients with response	Never	0	Always stop

Multc Lean Desktop (version 2.1.0) was used to generate the toxicity and futility stopping boundaries and the OC table (Table 10). In order to utilize the software for the design, a response constant rate of 5% and beta (0.1, 1.9) prior were assumed for the standard treatment response rate and experimental treatment response prior distribution, respectively. A delta 15% was assumed. In addition, a 30% toxicity constant rate and beta (0.6, 1.4) priors were assumed for the standard treatment toxicity rate and experimental treatment toxicity prior distribution, respectively.

The probability of stopping the study early if the true ORR of the combination treatment was 20% and the true toxicity rate was 30% was 18%. Probabilities of stopping early for high true toxicity rates (i.e., 50%) were 82% when the true ORR was 5% and 61% when true ORR rate was 20%.

Table 10. Operating characteristics for simultaneous monitoring response and toxicity rates for patients treated with combination treatment		
True Toxicity Rate	True ORR	Prob(stop the trial early)
0.10	0.05	0.5990
	0.10	0.3491
	0.15	0.1973
	0.20	0.1079
	0.25	0.0569

Table 10. Operating characteristics for simultaneous monitoring response and toxicity rates for patients treated with combination treatment

True Toxicity Rate	True ORR	Prob(stop the trial early)
0.20	0.05	0.6040
	0.10	0.3573
	0.15	0.2075
	0.20	0.1192
	0.25	0.0688
0.30	0.05	0.6326
	0.10	0.4037
	0.15	0.2647
	0.20	0.1828
	0.25	0.1360
0.40	0.05	0.7085
	0.10	0.5268
	0.15	0.4166
	0.20	0.3516
	0.25	0.3145
0.50	0.05	0.8230
	0.10	0.7126
	0.15	0.6456
	0.20	0.6062
	0.25	0.5836

Previously untreated MDS cohort

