Multc Lean Desktop (version 2.1.0) was used to generate the toxicity and futility stopping boundaries and the OC table (Table 13) In order to utilize the software for the design, a response constant rate of 50% and beta (1.0, 1.0) priors were assumed for the standard treatment response rate and experimental treatment response prior distribution, respectively. A delta 20% was assumed. In addition, a 30% toxicity constant rate and beta (0.6, 1.4) priors were assumed for the standard treatment toxicity rate and experimental treatment toxicity prior distribution, respectively.

The probability of stopping the study early if the true ORR of the experimental treatment was 70% and the true toxicity rate was 30% was 16%. Probabilities of stopping early for high true toxicity rates (i.e., 50%) were 81% when the true ORR was 50%, and 60% when true ORR rate was 70%.

Table 13. Operating characteristics for simultaneous monitoring response and toxicity rates for patients treated with combination treatment

True Toxicity Rate	True ORR	Prob(stop the trial early)
0.10	0.50	0.5590
	0.60	0.2740
	0.70	0.0850

Table 13. Operating characteristics for simultaneous monitoring response and toxicity rates for patients treated with combination treatment

True Toxicity Rate	True ORR	Prob(stop the trial early)
	0.80	0.0138
	0.90	0.0012
0.20	0.50	0.5646
	0.60	0.2831
	0.70	0.0965
	0.80	0.0262
	0.90	0.0138
0.30	0.50	0.5960
	0.60	0.3349
	0.70	0.1618
	0.80	0.0965
	0.90	0.0850
0.40	0.50	0.6795
	0.60	0.4723
	0.70	0.3349
	0.80	0.2831
	0.90	0.2740
0.50	0.50	0.8053
	0.60	0.6795
	0.70	0.5960
	0.80	0.5646
	0.90	0.5590

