8.2 Statistical Analysis Plan

Statistical Analysis Plan

All patients who received any dose of the study agent will be included in the analysis for efficacy and safety. Drop out of patients will count as failure for the efficacy analysis. Demographic/clinical characteristics (i.e. including duration of response) and safety data of the patients will be summarized using descriptive statistics such as mean, standard deviation, median and range. For the primary efficacy analysis, we will estimate the ORR (cohort 1) and ORR (cohort 2) for the combination treatment, along with the 95% credible interval. For the efficacy of cohort 1, a sample size of 20 patients ensures a posterior 95% credible interval for ORR of (0.06, 0.37), if the trial is not terminated early, under the assumption of a 20% ORR. For the efficacy of cohort 2, a sample size of 20 patients ensures a posterior 95% credible interval for ORR of (0.48, 0.85), if the trial is not terminated early, under the assumption of a 70% ORR. The association between ORR and patient's clinical characteristics will be

Product: MK-3475

60

Protocol/Amendment No.: 2016-0343 Amendment 2

examined by Wilcoxon's rank sum test or Fisher's exact test, as appropriate. Toxicity type, severity and attribution will be summarized for each patient using frequency tables. The distribution of time-to-event endpoints (EFS and OS) will be estimated using the method of Kaplan and Meier. Comparisons of time-to-event endpoints by important subgroups will be made using the log-rank tests. Paired t-tests will be used to determine the immunological and molecular changes in the peripheral blood and bone marrow from baseline to the time of response, and to the time of disease progression.

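### The HMA-failure ORR interval appears to reuse the futility prior Beta(0.1, 1.9); used after a 0/10 stop, it would report about (0%, 8%) where the exact interval is (0%, 31%)

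*Combined protocol and SAP*

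**What the plan says.** For the primary efficacy analysis, Section 8.2 states that "we will estimate the ORR (cohort 1) and ORR (cohort 2) for the combination treatment, along with the 95% credible interval". It does not say which prior produces that interval. For the cohort with the 20% target it adds that "a sample size of 20 patients ensures a posterior 95% credible interval for ORR of (0.06, 0.37", limited to a trial that is not terminated early and to an ORR of 20%. It gives (0.48, 0.85) for the other cohort at an ORR of 70%.

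The only ORR priors in the document are those in Section 8.1, given there as inputs to the monitoring software. For HMA failure, "a response constant rate of 5% and beta (0.1, 1.9) prior were assumed"; for untreated disease, "a response constant rate of 50% and beta (1.0, 1.0) priors were assumed". The HMA-failure cohort has a null ORR of 5%, a target of 20% and 20 patients. Its futility boundary (Table 9) is zero responses: "accrual will cease if no patients experience an overall response within 6 cycles in the first 10 patients treated".

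Section 8.2 includes every treated patient in the efficacy analysis. It gives no separate method for a cohort that stops early.

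**The concern.** Beta(0.1, 1.9) carries the weight of only two patients and has mean 5%, so it looks weak. Its shape is not weak near zero: its median is 0.04%, and 69% of its mass lies below an ORR of 1%. Once some responses are seen, this matters little. With no responses, the spike near zero largely sets the upper limit, and zero responses is the only result that triggers the futility stop.

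At stake is the primary estimate after a futility stop. A report giving an upper limit of about 8% would tell readers that ORRs of 10%, 15% and 20% are excluded at 95%, on ten patients.

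**Working it through.** **Inputs.** Priors, null (5%), margin (15 points), futility threshold (0.99), looks every 5 patients and the Table 9 boundary come from Section 8.1; the printed intervals come from Section 8.2. The posterior for x responses in n is Beta(a + x, b + n − x), with equal-tailed 2.5% and 97.5% quantiles.

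**1. Which prior gives the printed interval?** At 4/20:

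| Method | 95% interval |
|---|---|
| Beta(0.1, 1.9), posterior Beta(4.1, 17.9) | (0.057, 0.369) |
| Beta(0.5, 0.5), Jeffreys | (0.072, 0.408) |
| Beta(1, 1) | (0.082, 0.419) |
| Exact (Clopper-Pearson) | (0.057, 0.437) |
| Beta(0.1, 1.9), highest density | (0.044, 0.346) |

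Only the first rounds to (0.06, 0.37). As a cross-check, 14/20 under the untreated cohort's own design prior Beta(1, 1) gives (0.478, 0.854), which is the printed (0.48, 0.85). Both printed intervals therefore match the monitoring priors.

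**2. Is the stopping rule as understood?** Pr(ORR < 0.20) under Beta(0.1, 1.9) is 0.988 at 0/5 (continue), 0.997 at 0/10 (stop), 0.897 at 1/10 and 0.965 at 1/15 (continue). This is Table 9. Exact enumeration also reproduces all 25 cells of Table 10.

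**3. What would be reported at 0/10?**

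| Method | Upper 95% limit |
|---|---|
| Beta(0.1, 1.9), posterior Beta(0.1, 11.9) | 8.2% |
| Jeffreys | 21.7% |
| Beta(1, 1) | 28.5% |
| Exact | 30.8% |

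**4. How often does this happen?** P(0/10) = (1 − p)^10, which is 59.9% at p = 5%, 34.9% at 10%, 19.7% at 15% and 10.7% at 20%.

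**5. Coverage over the design.** Assume a stop at 0/10 with exactly 10 analysed, otherwise n = 20, and no toxicity stop. Coverage is 1 minus the probability of every path whose interval misses p. The 0/10 interval misses any p above 8.2%.

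- 10%: 1 − 0.349 (0/10) − 0.011 (lower limit above p) = 64.0%
- 12%: 1 − 0.278 − 0.007 = 71.5% (0.7148 before rounding, so 71%)
- 15%: 1 − 0.197 − 0.006 = 79.7%
- 20%: 1 − 0.107 − 0.029 (1/20, upper limit 17.0%) − 0.010 = 85.4%

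At 5% and 8%, coverage is 98.5% and 98.2%. Adding an independent toxicity stop (true toxicity 10% or 30%) gives 64.0-65.1%, 78.9-79.7% and 85.0-85.4% at ORRs of 10%, 15% and 20%.

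**6. Cohorts that reach n = 20.** Conditional on not stopping, the same interval covers 98.3%, 99.3% and 95.7% at 10%, 15% and 20%.

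**7. Alternatives under the same design.**

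| True ORR | Design prior | Jeffreys | Exact |
|---|---|---|---|
| 10% | 64% | 96% | 99% |
| 15% | 80% | 98% | 98% |
| 20% | 85% | 97% | 99% |
| 22% | 88% | 88% | 98% |
| 25% | 87% | 89% | 98% |

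Jeffreys moves the drop to just above its own 21.7% limit. The exact interval has a step too, just above 30.8%, but 0/10 is rare there: at 31.5%, 0.685^10 = 2.3%, and coverage is 95.0%.

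**The case against.** **The prior is inferred.** Correct. Section 8.2 names none, and the match is to a planning illustration limited to completed cohorts. A reader might infer that the plan commits itself to (0%, 8%) after a futility stop. It does not: it prints no interval for that case. But both printed intervals point to the design priors, no other ORR prior appears, and no other method is given for a stopped cohort.

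**A credible interval does not promise frequentist coverage.** This also stands. The 64-85% describes how this prior and this stopping rule behave together, and is not an arithmetic error. However, the prior is introduced to run the monitoring software and is nowhere justified as a belief for estimation, yet at 0/10 it sets the upper limit.

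**The shortfall is one outcome.** True, as steps 5 and 6 show. A reader might infer that the interval is unsound throughout. The documents' figures do not support that: for completed cohorts it is acceptable at 10-20%, and at ORRs of 5-8% the design-wide coverage is about 98%.

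**Overrun.** Response is judged after 6 cycles, so more than 10 patients may be treated by the time 0/10 is known. If 15 are analysed, coverage rises to 78%, 91% and 93% at 10%, 15% and 20%. The drop also moves lower: 0/15 would read (0%, 5.8%) and would miss a true 8% with probability 0.92^15 = 29%.

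**No decision changes.** Accrual stops at 0/10 whichever interval is printed, and the raw 0/10 is visible. This limits the severity.

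**Conclusion.** The concern holds in a limited form. The primary analysis has no stated prior; the printed interval indicates that the futility prior is being reused. If that reuse extends to a futility stop, the primary interval at 0/10 would have an upper limit of 8.2% against an exact 30.8%, and design-wide coverage would be 64% to 85% at true ORRs of 10% to 20%. Nearly all the shortfall comes from 0/10, and nearly all errors are in one direction, with the upper limit below the truth.

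This rests on three assumptions: Beta(0.1, 1.9) is the analysis prior, it is applied unchanged after a stop, and exactly 10 patients are analysed then. The plan's arithmetic, boundaries and Table 10 are not in question.

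The word for what 20 patients guarantee is a smaller matter of drafting. The printed limits arise only at exactly 4/20, which has probability 0.22 at a true ORR of 20%. Severity: should-fix.

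**What to change.** In Section 8.2:

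1. State that Beta(0.1, 1.9) serves the futility boundary only.
2. Report the HMA-failure ORR with an exact (Clopper-Pearson) 95% interval on all treated patients, including after an early stop. The design-prior credible interval may be shown beside it if its prior is named. Jeffreys is less suitable because of its 88-89% coverage at ORRs of 22-25%.
3. Replace the claim that 20 patients guarantee (0.06, 0.37) with: (0.06, 0.44) if 4 of 20 respond.
4. Reconcile the cohort numbering. Section 2.0 calls HMA failure cohort 2, while Section 8.2 attaches the 20% ORR to cohort 1.

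The cost is a few sentences and a planning interval whose upper limit moves from 0.37 to 0.44. The exact interval is also conservative, with about 98-99% coverage at 10-25%. No patients are added and no boundary changes.

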4.2.1 Rationale for the Trial and Selected Subject Population

Our hypothesis is that hematopoietic cells from patients with MDS express PDL1 after treatment with azacitidine and may therefore benefit from immune checkpoint therapy. We plan to study two different cohorts of patients. One will consist of a group of patients with previously untreated disease and the second cohort of patients with prior HMA exposure. These two cohorts will be treated in parallel (see statistical design). The reason to treat these two groups of patients in two different cohorts is due to the fact that patients with HMA failure are known to have a very distinct natural history than previously untreated patients(3). The survival of the groups of patients with HMA failure is documented to be 4 to 6 months (3). Also the expectation of response to any therapy has been significant lower in the group of patients with HMA failure (3).

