The target ORR with the experimental treatment is 70%, assuming the standard treatment ORR is 50%. The regimen of the experimental treatment will be considered worthy of further investigation if it elicits an increase in ORR to 70% with acceptable toxicity. A >30% therapy related non-hematological grade 3/4 toxicity rate is considered unacceptable. Thus, interim monitoring rules, assuming the prior distributions below, were constructed that meet the following two conditions,

- 3) Stop if $\text{Prob}\{p(\text{ORR}, E) < p(\text{ORR}, H) + 0.20 \mid \text{data}\} > 0.95$, or
- 4) Stop if $\text{Prob}\{p(\text{TOX}, E) > 0.30 \mid \text{data}\} > 0.95$,

where $p(\text{ORR}, E)$ and $p(\text{TOX}, E)$ are the true ORR and toxicity rates for the combination treatment, and $p(\text{ORR}, H)$ is the true ORR rate of the standard treatment. The first rule provides for stopping the study if the data suggest that it is unlikely (i.e., probability < 5%) that ORR rate of the experimental treatment is greater than the ORR rate of standard treatment by 20%. The second condition will stop the study early if excessive therapy-related

non-hematological grade 3/4 toxicity (>30%) is highly probable (i.e., probability >95%) for the experimental treatment. Monitoring for toxicity and futility will start with the first patient, and cohort size of 5.

The monitoring rule for the toxicity rate, based on these assumptions and monitoring conditions above is found in Table 11. For example, accrual will cease if 4 or more patients experience toxicities among the first 5 patients.

Table 11. Stop accrual if the number of drug-related non-hematological grade 3/4 toxicities is greater than or equal to indicated (i.e., # patients with toxicities) among the number of patients evaluated

# patients evaluated	5	10	15	20
# patients with toxicities	4-5	6-10	8-15	Always stop

Monitoring the ORR rate, based on the above assumptions and monitoring conditions is found in Table 12. For example, accrual will cease if 1 patients experience an overall response within 6 cycles in the first 5 patients treated.

Table 12. Stop accrual if the number with response is less than or equal to indicated (i.e., # patients with overall response) among the number of patients evaluated

# patients evaluated	5	10	15	20
# patients with response	0-1	0-4	0-7	Always stop

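### Section 8.2 leaves cohort out of the ORR association tests and subgroup log-rank tests; run on both cohorts combined, these can make an unrelated characteristic look predictive

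*Combined protocol and SAP*

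**What the plan says.** Section 8.2 sets one analysis population: "All patients who received any dose of the study agent will be included in the analysis for efficacy and safety". It then brings in cohort for one purpose: "For the primary efficacy analysis, we will estimate the ORR (cohort 1) and ORR (cohort 2) for the combination treatment", with a credible interval for each.

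The analyses that follow do not mention cohort:

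- Response: "The association between ORR and patient's clinical characteristics will be" "examined by Wilcoxon's rank sum test or Fisher's exact test, as appropriate".
- EFS and OS: Kaplan-Meier estimation, then "Comparisons of time-to-event endpoints by important subgroups will be made using the log-rank tests". The subgroups are not listed.

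No stratified or adjusted test appears anywhere in the document. Section 5.4 says the trial has no stratification, but that section concerns allocation and sets no rule for analysis.

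Elsewhere the plan treats the cohorts as very different. Section 4.2.1 explains that they are studied separately because "patients with HMA failure are known to have a very distinct natural history than previously untreated patients", and it expects a lower response after HMA failure. Section 8.1 sets the target ORR at 20% for HMA failure and 70% for untreated patients, with 20 patients in each cohort.

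**The concern.** By the plan's own assumptions, cohort is a very strong predictor of response and survival. A test that ignores it mixes two populations. If a characteristic is commoner in one cohort, the combined table gives it part of the difference between cohorts, even when it has no effect within either.

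Some imbalance is plausible. Sections 5.1.2 and 5.1.3 define the HMA-failure cohort by treatment history, and Section 4.2 reports PD1/PDL1 expression rising on HMA therapy, particularly after failure. A false predictor found in this way could be carried into patient selection for a later study.

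**Working it through.** **The plan's own figures.** With 20 patients, an ORR of 20% is 4 responders and 70% is 14. Using the priors in Section 8.1, equal-tailed 95% posterior intervals are:

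- HMA failure: Beta(0.1+4, 1.9+16) gives (0.057, 0.369); Section 8.2 states (0.06, 0.37).
- Untreated: Beta(1+14, 1+6) gives (0.478, 0.854); Section 8.2 states (0.48, 0.85).

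These reproduce. They are computed cohort by cohort, so the present point does not touch them.

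**Inputs from the documents.** 20 patients per cohort; ORR 20% and 70% (Section 8.1); survival of 4 to 6 months after HMA failure (Section 4.2.1); median survival of 24.4 months on azacitidine in the cited phase III trial (Section 4.1.1, Azacitidine), used as a proxy for the untreated cohort.

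**Assumptions not in the documents.** A binary characteristic with prevalence q1 in HMA failure and q2 in untreated patients, independent of outcome within each cohort; two-sided 5% tests; for survival, exponential times and censoring uniform over 12 to 36 months. That range fits the Trial Summary: a 36-month trial with 24 months of enrolment leaves 36 − 24 = 12 months for the last patient.

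**Step 1: the apparent difference in ORR.** With equal cohort sizes, the expected combined ORR is

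- with the characteristic: (0.2·q1 + 0.7·q2) / (q1 + q2)
- without it: (0.2·(1−q1) + 0.7·(1−q2)) / (2 − q1 − q2)

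At 70/30 these are (0.14 + 0.21)/1 = 35% and (0.06 + 0.49)/1 = 55%. The true within-cohort difference is zero, so the 20-point gap is entirely due to cohort.

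**Step 2: how often the response test rejects.** 20,000 simulated trials per row; CMH is stratified by cohort, without continuity correction.

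| q1/q2 (%) | Expected combined ORR, with / without | Pooled Fisher rejects | CMH rejects |
|---|---|---|---|
| 50/50 | 45% / 45% | 2.7% | 5.0% |
| 60/40 | 40% / 50% | 6.1% | 4.9% |
| 70/30 | 35% / 55% | 17.3% | 4.6% |
| 75/25 | 32.5% / 57.5% | 27.1% | 4.6% |
| 80/20 | 30% / 60% | 37.7% | 4.4% |

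The simulation error at 70/30 is √(0.173 × 0.827 / 20,000) = 0.27 percentage points. Repeat simulations gave 6.0-6.3% at 60/40, 17.1-17.3% at 70/30 and 26.7-27.1% at 75/25.

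Over 50/50 to 80/20, CMH with continuity correction rejects 1.1-1.8% and Fisher within a single cohort 1.4-2.1%.

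**Step 3: log-rank.** Medians of 5 and 24.4 months, 4,000 simulated trials per row; in brackets, HMA-failure medians of 6 and 4 months (2,000 trials each).

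| q1/q2 (%) | Pooled log-rank rejects |
|---|---|
| 50/50 | 5.6% |
| 60/40 | 11.9% |
| 70/30 | 32.3% (28-38%) |
| 80/20 | 62.4% (56-72%) |

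Stratified by cohort, the log-rank test rejects about 5-7% throughout, including simulation error. These figures lean on more assumptions than those in Step 2 and should be taken as indicating direction and rough size.

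**The case against.** A reader might infer that the SAP prescribes pooled tests. It does not: 8.2 never says that the cohorts are combined. The all-treated sentence only settles who is evaluable, and it equally governs the primary ORR estimate, which is by cohort. Endpoint, targets, priors, boundaries and operating characteristics are all set separately for each cohort in 8.1, so an analyst could reasonably run Fisher and Wilcoxon within cohort and comply. This stands. The gap is a missing statement on cohort. But a within-cohort reading is not written either, and the tests as named, applied to all treated patients, are open to confounding.

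The prevalences are hypothetical. The cohorts share the same IPSS, age, ECOG and organ-function criteria, and no document gives a basis for an imbalance as large as 70/30. This stands too: the rates are a range, and at equal prevalence there is no inflation. A reader might also infer that combined tests would mostly rediscover cohort membership. The figures do not support that in general: at 70/30 pooled Fisher fails to reject about 83% of the time.

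The unlisted subgroups could include cohort itself, and comparing the two cohorts by log-rank would be legitimate. The fix has to leave room for that.

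Finally, these tests carry no hypothesis, alpha or decision. That limits the seriousness, but an exploratory label alone does not remove confounding, and survival effect is named in the second objective of Section 3.1.

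**Conclusion.** The point holds as a gap in specification with a cheap remedy. 8.2 permits unstratified tests across two cohorts that the plan expects to differ by 70% − 20% = 50 percentage points in ORR. If they are run that way, false-positive rates range from none above nominal at equal prevalence to about 17% at 70/30 and 27% at 75/25 for Fisher, and higher for log-rank under the survival assumptions used. The size depends wholly on prevalences that the documents do not supply.

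A reader should not extend this to the main results. The cohort ORR estimates, their credible intervals and the stopping rules are built within cohort and are unaffected. The consequence is confined to secondary analyses.

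**What to change.** First reconcile the cohort numbering. Section 2.0 makes cohort #1 the previously untreated patients, whereas 8.2 gives cohort 1 the interval for a 20% ORR, which 8.1 sets for HMA failure. Cohort cannot safely be named as a stratum until this is settled.

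Then add to 8.2 that:

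- the ORR association tests and the EFS and OS subgroup comparisons are done within cohort and labelled exploratory;
- any combined test is stratified by cohort: CMH or an exact stratified test for categorical factors, van Elteren for continuous or ordered factors, stratified log-rank for EFS and OS;
- the exception is a comparison in which cohort is itself the subgroup.

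This takes a sentence or two and no new data. The cost is power: Fisher within a cohort of 20 is conservative, rejecting about 2% at nominal 5%. A characteristic found in only one cohort, such as prior HMA exposure, gives a stratified test nothing to compare; variation in treatment history can be studied only within the HMA-failure cohort.

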4.2.4.2 Biomarker Research

Correlative studies will be considered exploratory and will be performed whenever possible. This will be voluntary. Patients will have opportunity to refuse participation on these studies. If a patient's baseline correlative bone marrow or blood sample is not collected for any reason, no additional correlative bone marrow or blood samples will be collected on the patient. Additionally, any samples that are missed are not considered a protocol deviation.

Gene sequencing.

Patients will be consented for genomic analysis according to institutional guidelines. At MD Anderson, patients not consented through the Apollo program (PI [name]) will be offered consenting under protocol LAB01-473 at baseline and their genomes will be sequenced using the T300 platform. 5 cc of blood in a green tube will be required for this analysis.

These samples will be obtained at baseline and on Cycle 1 day 28 (+/- 3 days) (including analysis of the bone marrow) every 3 cycles thereafter, and at the time of best morphological response.

Immune assessment.

Tumor tissue, blood samples and bone marrow aspirate will be collected on a separate IRB approved laboratory protocol (PA13-0291) for immune monitoring under the supervision of the Immunotherapy Platform at MD Anderson Cancer Center. In tumor tissues, immunohistochemical studies will be performed to evaluate tumor and immunological cell markers such as CD4 and CD8 T cells. In peripheral blood, we will also evaluate tumor and immune cell populations including but not limited to CD4 and CD8 T cells in pre and post therapy samples.

Peripheral blood

Up to 150 mL (within 24 hours) of peripheral blood will be collected under an IRB-approved laboratory protocol (PA13-0291) for testing of biomarkers described in this clinical protocol at the following time points:

- At screening
- Prior to each dose of MK3475 (pembrolizumab) during the first 3 cycles
- At time of best morphological response
- At progression

Product: Pembrolizumab

Protocol/Amendment No.: 2016-0343 Amendment 3.4

The treating physician or designee will have the option to cancel the laboratory protocol collection for patient safety without protocol deviation.

Analysis of hematopoietic stem cell populations

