We will also analyze the effect of therapy at the level of different stem cell compartments (15). This will be done in the laboratory of [name] at MD Anderson Cancer Center. This will be done at baseline and Cycle 1 Day 28 and then every 3 months thereafter.

Because we will use a number of different assays, the variability of which is not necessarily established, the intention of the correlative studies is not to draw statistical conclusions in terms of the optimal biological dose of the agents studied here. Rather, they should be considered pilot studies that will help understand the in vivo mechanism of action of the agents studied, and may help in the development of future studies of this or other combinations.

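### Section 8.2 tests biomarker change only at response and at progression, and plans no analysis of the on-treatment samples drawn at scheduled times

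*Combined protocol and SAP*

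**What the plan says.** Section 8.2 gives one analysis for the correlative data: paired t-tests for immunological and molecular "changes in the peripheral blood and bone marrow from baseline to the time of response, and to the time of disease progression". No other time point is named. The sentence does not say whether the cohorts are analysed separately or pooled, and it states no significance level or power.

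The collection plan is wider. Section 4.2.4.2 says of the gene sequencing samples: "These samples will be obtained at baseline and on Cycle 1 day 28", and then every 3 cycles. Immune-monitoring blood is drawn at screening, then "Prior to each dose of MK3475 (pembrolizumab) during the first 3 cycles", and again at best morphological response and at progression. Of the stem-cell work it says: "This will be done at baseline and Cycle 1 Day 28 and then every 3 months thereafter". The footnotes to the flow chart in Section 6.1 repeat the blood schedule and place marrow correlatives at days 22 to 28 of cycles 1 and 3, then every 3 cycles.

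The same section makes participation voluntary, stops later correlative sampling if the baseline sample is missing, and does not count a missed sample as a deviation. It describes the correlative work as exploratory pilot studies meant to help explain mechanism. The objective they serve, in Section 3.2, concerns the biological effects of the combination in patients treated on the study, not in responders alone.

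**The concern.** A test at the time of response can use only responders, and a test at progression only progressors. The interval from baseline differs from patient to patient in both. A change seen this way mixes three things: drug exposure, length of exposure, and having been selected for the outcome. Responders and non-responders are never compared at a common time.

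This fits poorly with the hypothesis in Sections 3.1 and 4.2.1, that azacitidine raises PD1/PDL1 expression and so primes cells for checkpoint inhibition. That predicts a change on treatment in patients generally. The scheduled samples could show it most directly, and they have no stated analysis. The consequence is confined to the exploratory objective; no stopping rule or efficacy conclusion uses these tests.

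**Working it through.** **Inputs from the documents.** Section 8.1: "Each cohort will be composed of N=20 patients"; in the HMA-failure cohort the target ORR is 20% and the null 5%, with a Beta(0.1, 1.9) response prior; in the previously untreated cohort the target is 70%, with a Beta(1, 1) prior. Section 8.2 attaches the 20% rate to cohort 1, whereas Section 2.0 numbers the previously untreated patients as cohort 1. The cohorts are therefore named here by disease status.

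**Inputs assumed.** Two-sided 5% level and 80% power. Effects are in SDs of the within-patient change.

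**Step 1: reproduce the plan's own figures.** The documents give no figure for the t-tests, but the credible intervals in Section 8.2 show the responder counts in use.
- HMA failure, 4 of 20: Beta(0.1 + 4, 1.9 + 16) = Beta(4.1, 17.9), equal-tailed 95% interval (0.057, 0.369). The plan states (0.06, 0.37).
- Previously untreated, 14 of 20: Beta(1 + 14, 1 + 6) = Beta(15, 7), interval (0.478, 0.854). The plan states (0.48, 0.85).

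**Step 2: pairs available at response in the HMA-failure cohort**, if it enrols all 20 patients.
- Target: 20 × 0.20 = 4. With X ~ Bin(20, 0.20), P(X ≤ 2) = 0.206.
- Null: 20 × 0.05 = 1. With X ~ Bin(20, 0.05), P(X ≤ 1) = 0.736.

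These counts precede any loss from refusal or missed samples. There is a further uncertainty: ORR includes hematological improvement, while the response sample is tied to best morphological response.

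**Step 3: detectable change.** For n pairs and standardized mean change δ, with c the 97.5% point of t on n − 1 degrees of freedom, power = P(|T| > c), where T is non-central t with n − 1 degrees of freedom and non-centrality δ√n. Solving for power = 0.80:

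| Pairs | Example | δ at 80% power | Power at δ = 1 |
|---|---|---|---|
| 4 | HMA-failure responders at target | 2.13 | 29% |
| 10 | half of one cohort (assumed) | 1.00 | 80% |
| 14 | untreated responders at target | 0.81 | 93% |
| 18 | responders of both cohorts pooled (4 + 14) | 0.70 | 98% |
| 20 | one full cohort, scheduled time | 0.66 | 99% |

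**Step 4: match scheduled times to assays.** Cycle 1 day 28 is a scheduled time for genomic and stem-cell work, and marrow correlatives fall at days 22 to 28 of cycle 1. Immune blood is not drawn then. Three 4-week cycles with pembrolizumab every 3 weeks put its pre-dose draws at about days 1, 22, 43 and 64. A fixed-time analysis therefore has to be set assay by assay.

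**The case against.** The strongest reply is that these are voluntary pilot studies, done when feasible, with assays whose variability is not established, so 80% power is not the standard they were designed to. That stands, and it keeps the point minor. It does not supply the missing analysis: the disclaimer of statistical conclusions in Section 4.2.4.2 is worded for optimal biological dose, the same text gives mechanism as the aim, and Section 8.2 does name tests.

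A reader might infer that the plan yields almost no biomarker information in the HMA-failure cohort. The documents do not support that. The 4 pairs limit only the response contrast. At a 20% ORR, 16 of 20 patients do not respond, and blood is scheduled at progression. The number of progression pairs is not given; if it were 10 to 14, the detectable change would be 1.00 to 0.81 SD. That contrast nevertheless remains selected on outcome and taken at varying times. Response and progression samples also have a proper use for the resistance part of the hypothesis.

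Pooling is not excluded by Section 8.2, and 18 pooled responders would detect 0.70 SD. But 14 of the 18 would be previously untreated, Section 4.2.1 separates the cohorts because their natural histories differ, and selection on response would remain.

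Voluntary sampling cuts both ways. The 20 pairs at a scheduled time are a ceiling, as are the 4 at response, and no participation rate is stated.

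**Conclusion.** The point holds as a minor one. The stated contrasts are conditioned on outcome, and the scheduled on-treatment samples have no planned analysis, although the objective concerns patients treated on the study. Under separate analysis by cohort, two-sided 5% and 80% power (all assumptions), moving from the response contrast to a scheduled time in the HMA-failure cohort lowers the detectable change from 2.13 SD (4 pairs) to between 1.00 SD (10 pairs) and 0.66 SD (20 pairs), depending on participation. In the untreated cohort the gain is smaller: 0.81 SD (14 pairs) to 0.66 SD (20 pairs).

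A reader might also infer that a fixed-time change would show what the combination does. It would not. Both drugs start on cycle 1 day 1 and there is no control group, so a scheduled contrast removes selection on outcome but cannot separate the combination's effect from that of azacitidine alone.

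**What to change.** In Section 8.2:
- Make the main biomarker analysis the change from baseline at each assay's own scheduled times, within each cohort, in all patients with a baseline and an on-treatment sample. For immune blood, use the pre-pembrolizumab draws in cycles 1 to 3. For marrow, genomic and stem-cell assays, use the end-of-cycle-1 sample (days 22 to 28) and the later scheduled samples.
- Use a paired test at a named time or a mixed model over the scheduled times, and report the number of pairs at each.
- Compare responders with non-responders descriptively at the same times.
- Keep the response-time and progression-time changes as descriptive summaries.
- State that an uncontrolled change at a fixed time does not isolate the combination's effect from azacitidine's.

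The cost is SAP wording and slightly more analysis. No samples, visits or patients are added, and the primary analysis is untouched.
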